8.1.2. PK Parameters

The analytes and parameters presented in [Table 8-1](#) will be used to evaluate the PK objectives of the study. The PK parameters to be estimated in this study are listed and defined in the PK Abbreviations section.

Table 8-1. PK Parameters for VES

| Analyte | Parameters |
|-------------|--|
| VES | AUC_{inf} , AUC_{last} , AUC_{exp} , C_{max} , T_{max} , C_{last} , T_{last} , $t_{1/2}$, CL/F , and V_z/F |
| VRC07-523LS | AUC_{inf} , AUC_{last} , AUC_{exp} , C_{max} , T_{max} , C_{last} , T_{last} , $t_{1/2}$, CL , V_{ss} , and V_z |
| CAP256V2LS | AUC_{inf} , AUC_{last} , AUC_{exp} , C_{max} , T_{max} , C_{last} , T_{last} , $t_{1/2}$, CL , V_{ss} , and V_z |

8.1.3. Statistical Analysis Methods

Individual participant concentration data and individual participant PK parameters for VES, VRC07-523LS, and CAP256V2LS will be listed and summarized using descriptive statistics for participants in the corresponding analyte PK analysis set. Summary statistics (number of participants, mean, SD, CV, median, min, max, Q1, and Q3) will be presented for both individual participant concentration data by time point and individual participant PK parameters. For individual participant concentration data for VRC07-523LS and CAP256V2LS, the summaries will only be presented through end of Period 3, since the actual time from study drug dosing varies depending on the time of ART restart for visits after end of Period 3 visit. Moreover, the geometric mean, geometric mean coefficient of variation (GCV), 95% CI for the geometric mean, and the mean and SD of the natural log-transformed values will be presented for individual participant PK parameter data.

Individual concentration data listings and summaries will include all participants with concentration data. If a participant has quantifiable pre-dose, BLQ at end of infusion, or received an incorrect dose, the related PK concentration(s) will be included in the table but will be excluded from the summary statistics, with reasons for exclusion identified. The sample size for each time point will be based on the number of participants with non-missing concentration data at that time point. The number and percentage of participants with concentration BLQ, as well as an indicator if more than one-third of the participants have concentration BLQ, will be presented for each time point. For summary statistics, BLQ values will be treated as zero at baseline and postdose time points. The method to handle BLQ values for PK summaries are described in Section 3.7. Concentration values will be presented as received from the bioanalytical lab and summary statistics will be presented to three significant digits.

Individual PK parameter data listings and summaries will include all participants for whom PK parameter(s) can be derived. The sample size for each PK parameter will be based on the number of participants with non-missing data for that PK parameter. PK parameters could be unestimatable due to insufficient concentration data or may be estimated but marked for exclusion due to reasons such as the participant received an incorrect dose. In such cases, the PK parameters will be included in the table but will be excluded from the summary statistics, with reasons for exclusion identified.

The following tables will be provided for each analyte:

- Individual participant concentration data and summary statistics
- Individual participant plasma/serum PK parameters and summary statistics

The following figures may be provided for each analyte:

- Mean (\pm SD) concentration data versus time (on linear and semilogarithmic scales)
- Median (Q1, Q3) concentration data versus time (on linear and semilogarithmic scales)

- Individual participant plasma/serum concentrations versus time (on linear and semilogarithmic scales)

Individual, mean, and median postdose concentration values that are BLQ will not be displayed in the figures and the remaining points will be connected.

PK sampling details by participant, including differences in scheduled and actual collection times and sample age, will be provided in listings. In addition, determination of half-life and corresponding correlation coefficient will be listed.

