1.4.3. Rationale for Dose Selection of VRC07-523LS

Dose selection for VRC07-523LS is supported by PK and safety data from the completed Study VRC605 and the ongoing Study VRC607. In these studies, IV administration of VRC07-523LS single dose up to 40 mg/kg has been shown to be safe and well tolerated. The proposed dose of 20 mg/kg IV administered on Day 7 is predicted to provide concentrations of VRC07-523LS > 20 µg/mL through the end of Period 2 (Week 19); 20 µg/mL VRC07-523LS is approximately 100-fold higher than the in vitro IC₈₀, corresponding to a predicted > 80% neutralization coverage of sensitive HIV viruses {[Gaudinski 2019](#)}. In Period 3, VRC07-523LS concentrations are predicted to be subtherapeutic (< 20 µg/mL), allowing the assessment of viral control potentially resulting from HIV reservoir reduction and/or immunologic control.

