- l VRC07-523LS and CAP256V2LS sequential dose administration to occur only once at Day 7.

During Period 1, VRC07-523LS, CAP256V2LS, and VES will be administered together with ART.

Sentinel Dosing: Participants will be enrolled and dosed in a staggered fashion, with a sentinel group consisting of 5 participants conducting Period 1 visits and assessments up to Day 21 first. The safety data of the first 5 participants will be reviewed by an external DMC, and upon confirmation, up to a further 20 participants will be enrolled into Period 1.

During Period 2, the participants will be administered VES and discontinue ART to start ATI with weekly plasma virus monitoring at each study visit.

In Period 3, no treatment (VES, VRC07-523LS, CAP256V2LS, or ART) will be administered, participants will continue ATI and plasma virus levels will be monitored.

At the end of Period 3 or if ART restart criteria are met prior to starting Period 4A, participants will be required to complete an end-of-Period 3 visit.

In Period 4, participants who have remained virologically suppressed (plasma HIV-1 RNA < 50 copies/mL) or have not met the ART restart criteria by the end of Period 3 will continue in either Period 4A and restart ART for 12 weeks, or in Period 4B and remain off ART for a 12-week ATI extension. The choice of Period 4A or 4B will be at the discretion of the participant and investigator.

If the ART restart criteria are met prior to the end of Period 3, participants may also receive ART for 12 weeks in Period 4A.

At the end of Period 4, all participants will complete an end-of-study visit.

If a participant should discontinue study dosing as described in Section [6.9.1](#), they will be required to complete an early study drug discontinuation (ESDD) visit and every attempt should be made to keep the participant in the study and continue to perform study procedures. If the participant is unable to complete all scheduled procedures, for criteria other than those described for study discontinuation in Section [3.5](#), the participant should be followed by as described in Section [6.9.2](#).

If a participant has completed all study drug dosing but is unable to complete all subsequent visits at the study site, as scheduled in Periods 3 and 4, for criteria other than those described for study discontinuation in Section [3.5](#), the participant should be followed by telephone for up to 250 days after mAb infusion.

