6.3.3. ATI Eligibility Criteria

At the Day 28 visit and prior to the Period 2 Day 35 visit, participants will be assessed to determine whether the criteria necessary to begin ATI are met. All of the following criteria must be met for a participant to begin ATI (Period 2):

- Viral load < 50 copies/mL
- CD4+ T cell count > 400 cells/ μ L
- Negative urine pregnancy test
- Participant has received VRC07-523LS, CAP256V2LS, and at least 3 of the 10 scheduled doses of VES.
- Participant confirms agreement to request their partners to use condoms throughout the ATI period.

The initiation of ATI (Period 2) may be postponed for up to 4 weeks after the last VES dose for participants to meet the above requirements. If a participant develops any other acute event during this time that may require treatment before the participant starts the ATI (Period 2), the investigator should consult with the medical monitor. The investigator may delay the initiation of the ATI (Period 2), after consultation with the medical monitor, for up to a further 4 weeks if it is determined that the participant may proceed to ATI (Period 2) once the acute event has been treated successfully. The investigator should consult with the medical monitor to determine if repeat assessments should be performed to re-confirm the participant's eligibility for the ATI (Period 2).

Participants who do not meet the requirements for ATI (Period 2) will complete an ESDD visit within 3 days of informing the investigator/site and may undergo early discontinuation of study follow up and procedures as described in Section [6.9.2](#).

6.4. Treatment Assessments—Period 2

Participants will have up to 18 visits over 15 weeks. Doses 4 to 10 of VES will be administered orally on Day 42, Day 56, Day 70, Day 84, Day 98, Day 112, and Day 126.

For Doses 4 to 10, 6 mg [3x2 mg tablets] or 8 mg [4x2 mg tablets]) will be administered per discussion with and approval from the Gilead medical monitor based on safety and tolerability of prior doses.

Participants will remain at the site for monitoring for at least 4 hours after VES dosing. If participants experience significant influenza-like AEs (eg, moderate or severe pyrexia, chills, headache, myalgia, fatigue, malaise, joint pain) after the first 2 VES doses, monitoring may be extended to > 4 hours for subsequent doses. Fasted status and food consumption will be checked prior to dosing.

No ART will be administered and ATI will start from Day 35.

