If the ART restart criteria are met, the end-of-Period 3 visit (Section 6.5.2) will be completed and the participant may begin Period 4A.

Table 4. Period 2 Study Visits and Study Drug Administration

ATI = analytical treatment interruption; VES = vesatolimod
Every Period 2 study visit is based on the Day 0 visit + the number of postponement days required to confirm ATI eligibility in Period 1, if applicable

6.4.1. Treatment Assessments—Days 29 to 133

The following assessments are to be completed at every visit, unless otherwise specified. All study visits are to be completed within ± 3 days of the protocol-specified visit date (based on the Day 0 visit + the number of postponement days required to confirm ATI eligibility in Period 1, if applicable), and study procedures are to be completed within ± 2 hours of the protocol-specified time point. Symptom-directed physical examination

- Vital signs (blood pressure, pulse, respiration rate, oxygen saturation, and temperature) at:
 - Doses 4 to 10 of VES prior to administration and at 1, 2, and 4 hours after administration
(Day 42 and at each visit every 2 weeks thereafter)
 - If the participant experiences new or worsening symptoms, evaluate for signs and symptoms of CRS, including vital signs
- Body weight (Day 42 and at each visit every 2 weeks thereafter)
- Obtain blood samples for:
 - Plasma HIV-1 RNA **(Day 42 and at each visit every 2 weeks thereafter)**
 - If a confirmed rebound of ≥ 50 copies/mL occurs, the test should be completed weekly

- Plasma HIV-1 resistance testing (in case of viral rebound) to VRC07-523LS, CAP256V2LS, and baseline ART (**Day 42 and at each visit every 2 weeks thereafter**)
- Chemistry profile: ALP, AST, ALT, total bilirubin, direct and indirect bilirubin, total protein, albumin, CK, bicarbonate, BUN, calcium, chloride, creatinine, glucose, phosphorus, magnesium, potassium, sodium, uric acid (**Day 42 and at each visit every 2 weeks thereafter**)
- Hematology profile: CBC with differential and platelet count (**Day 42 and at each visit every 2 weeks thereafter**)
- Creatinine clearance according to the Cockcroft-Gault formula (**Day 42 and at each visit every 2 weeks thereafter**):
$$\text{Female Estimated Creatinine Clearance} = [(140 - \text{age in years}) \times (\text{weight in kg})]/[72 \times (\text{serum creatinine in mg/dL})] \times 0.85$$
- Anti-VRC07-523LS and anti-CAP256V2LS antibody profiling from serum (**Days 56, 84, 112, and 133**)

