3.8.2. Analysis Visits

The nominal visit as recorded on the eCRF or lab date will be used when data are summarized by visit. Any data relating to unscheduled visits will not be assigned to a particular visit or time point and in general will not be included in by-visit summaries. However, the following exceptions will be made:

- An unscheduled visit prior to the first dose of study drug may be included in the calculation of baseline value, if applicable.
- Unscheduled visits after the first dose of study drug will be included in determining the maximum postbaseline toxicity grade and time to event analyses.
- For participants who prematurely discontinued from the study drug, early termination (ET) data will be summarized as a separate visit, labeled as “Early Study Drug Discontinuation”.
- Data obtained after the follow-up visit or last exposure date (whichever is later) will be excluded from the summaries but will be included in the listings.

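### SAP 8.1.3 treats time since infusion as common to all participants through Period 3, but a postponed ATI moves every Period 2 and 3 antibody sample by up to 21 or 49 days under the same visit label

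*SAP*

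**What the plan says.** For the two antibodies, SAP 8.1.3 states that "the summaries will only be presented through end of Period 3", and its reason is "since the actual time from study drug dosing varies depending on the time of ART restart for visits after end of Period 3 visit". The general visit rule in SAP 3.8.2 is: "The nominal visit as recorded on the eCRF or lab date will be used when data are summarized by visit". Protocol 8.7 likewise summarises concentrations by nominal sampling time.

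The design behind these rules is as follows.

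- Protocol 3.2, study schema footnote: "VRC07-523LS and CAP256V2LS sequential dose administration to occur only once at Day 7".
- Protocol 6.4: "No ART will be administered and ATI will start from Day 35".
- Protocol 6.3.3: the start of ATI "may be postponed for up to 4 weeks after the last VES dose". A further period of up to 4 weeks is possible for an acute event, after consultation with the medical monitor.
- Protocol 6.4 and 6.5, notes to Tables 4 and 5: each Period 2 and Period 3 visit is dated from Day 0 plus "the number of postponement days required to confirm ATI eligibility in Period 1, if applicable".

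The SAP's visit definitions (3.8.1 to 3.8.3) contain no rule for postponed participants.

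**The concern.** The SAP itself recognises that a by-visit concentration summary is hard to interpret when participants at that visit are at different times since dosing, and it drops the later visits for that reason. The same condition can arise earlier. A postponed participant keeps the nominal labels of Periods 2 and 3 but reaches each visit later after the Day 7 infusion. Eleven antibody sampling labels are exposed: Days 56, 84, 112, 133, 161, 189, 217, 245, 273, 301 and 329.

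At stake are the by-time-point tables and the mean and median concentration plots. The dose rationale in Protocol 1.4.2 and 1.4.3 rests on antibody cover in Periods 1 and 2 and its loss in Period 3. A reader will use these tables and plots to judge whether that happened. If they mix post-infusion times, they describe neither the planned profile nor the one that participants had.

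**Working it through.** **Inputs.** The infusion is on Day 7 and planned ATI start is Day 35. The last VES dose before ATI is Dose 3, on Day 28 (Protocol 6.3). The two allowances are 28 days each (Protocol 6.3.3). For VRC07-523LS at 20 mg/kg, Protocol Table 1 gives mean C28d 148 µg/mL, C84d 44 µg/mL and half-life 45 days; Protocol 1.2.6 gives an overall half-life of about 38 days. The documents give no human half-life for CAP256V2LS, so only VRC07-523LS is computed.

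**Size of the shift.** The ±3-day visit window is ignored.

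- First allowance: 28 + 28 = Day 56; 56 − 35 = 21 days.
- Both allowances: 28 + 28 + 28 = Day 84; 84 − 35 = 49 days.

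Nominal Day 56 is 56 − 7 = 49 days after infusion without delay, 70 days after a 21-day shift and 98 days after a 49-day shift.

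**The plan's own figure.** Protocol 1.4.3 predicts more than 20 µg/mL to Week 19 (Day 133, 126 days after infusion). With C(d) = 44 × 2^(−(d − 84)/t½) for d of 84 or more:

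- t½ = 45: 44 × 2^(−42/45) = 23.0 µg/mL
- t½ = 38: 44 × 2^(−42/38) = 20.5 µg/mL

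The prediction is reproduced, narrowly at 38 days. The steeper slope between C28d and C84d (half-life 56 × ln 2 / ln(148/44) = 32 days) would give 17.7 and does not reproduce it. So 38 and 45 days are used below.

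**The same label after postponement (nominal Day 133).**

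| Shift | Days since infusion | t½ = 45 | t½ = 38 |
|---|---|---|---|
| 0 | 126 | 23.0 | 20.5 |
| 21 | 147 | 16.7 | 13.9 |
| 49 | 175 | 10.8 | 8.4 |

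**Fold difference under one label, 2^(shift/t½).**

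- 21 days: 2^(21/45) = 1.38; 2^(21/38) = 1.47
- 49 days: 2^(49/45) = 2.13; 2^(49/38) = 2.44

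These ratios apply from nominal Day 112 on. Nominal Days 56 and 84 fall partly in the steeper phase before 84 days. Interpolating log-linearly between C28d and C84d gives 1.58 and 2.65 to 2.76 at Day 56, and 1.44 to 1.50 and 2.22 to 2.50 at Day 84.

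**Effect on a pooled mean.** The number postponed is not in the documents, so this step is an assumption. If k of 25 participants are postponed by the same shift, the mean falls by (k/25) × (1 − 2^(−shift/t½)).

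- k = 1: 1.1% to 1.3% for 21 days; 2.1% to 2.4% for 49 days
- k = 5: 5.5% to 6.4% for 21 days; 10.6% to 11.8% for 49 days
- k = 0: no effect

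The fold differences describe individual samples. The mean moves less unless many participants are postponed.

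**The case against.** The strongest reply is that little depends on these tables. The secondary PK endpoints are noncompartmental parameters, which SAP 8.1.1 estimates with actual times. SAP 8.1.3 also lists scheduled against actual collection times and tabulates individual concentrations. In a descriptive study of up to 25 women, a reader can recover each true interval. Day 84 also needs an acute event and a consultation, and postponement may be rare or absent. All of this is correct and limits the weight of the point. It does not repair the by-time-point summaries or the mean and median plots, which keep the nominal labels.

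A reader might infer more than the documents support, in three ways.

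- *That Kaplan-Meier time to rebound is biased towards a delay because it runs from ATI start.* ATI start is the protocol's own origin, since the endpoint is defined as following ATI. Postponed participants begin ATI with less antibody, so on this mechanism pooling them tends to shorten the curve and cannot create a spurious delay. A curve restricted to unpostponed participants would keep those with the most antibody cover and would not separate antibody effect from reservoir effect.
- *That no analysis relates rebound to antibody level.* Parts of the objectives, of the protocol's analysis section and of SAP 6.2 are blacked out, so absence cannot be claimed.
- *That the Week 19 prediction in Protocol 1.4.3 is wrong.* It reproduces on the planned schedule. By the formula above, the predicted mean stays above 20 µg/mL for shifts up to about 9 days (t½ 45) or about 1 day (t½ 38), and falls below for longer ones. It is a design prediction, and no SAP analysis uses it.

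**Conclusion.** The point holds for the by-time-point antibody concentration summaries and the mean and median plots in Periods 2 and 3. The reason that SAP 8.1.3 gives for stopping at the end of Period 3 applies equally, before that visit, to any participant whose ATI is postponed. The size is that shown in the working: individual predicted levels under one label differ by about 1.4- to 1.5-fold at the 21-day limit and 2.1- to 2.4-fold at the 49-day limit, and slightly more at the two earliest labels.

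This rests on mean values in healthy volunteers, log-linear decline after 84 days with a half-life of 38 to 45 days, and visits on their scheduled days. CAP256V2LS samples shift by the same number of days, but the fold difference cannot be computed from the documents. The number postponed is unknown. The point does not extend to the noncompartmental parameters, to the definition of time to rebound or to the protocol's dose rationale.

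**What to change.** In SAP 8.1.3:

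- Summarise and plot Period 2 and 3 VRC07-523LS and CAP256V2LS concentrations in windows of actual days since infusion. Alternatively, keep nominal visits but exclude postponed participants' samples or show them separately.
- Give postponement as a second reason why time from dosing varies, alongside ART restart.
- Tabulate days from infusion to ATI start, with the number of participants postponed.
- As a supportive display only, list each participant's antibody levels nearest ATI start and nearest rebound.

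Keep ATI start as the origin for time to rebound. No restricted Kaplan-Meier curve and no change to Protocol 1.4.3 is needed.

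The cost is SAP wording and re-windowing. Dosing dates, ATI start date (SAP 3.8.1) and actual sampling times are already collected or derived. The SAP is signed as version 1.0, so the change would go in as a revision under SAP 11 or, as SAP 1 provides for changes after finalisation, be documented in the study report. It needs no new data and alters no clinical rule. If nobody was postponed, a single sentence saying so is enough.

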8.2. Changes From Protocol-Specified PK Analyses

There are no changes from the protocol-specified PK analyses.

9. IMMUNOGENICITY ANALYSES

9.1. Definition of Terminology

Participants Evaluable for ADA Prevalence: participants who have at least one reportable ADA result at baseline or post-baseline.

Participants Evaluable for ADA Incidence: participants who have at least one reportable ADA result at post-baseline.

ADA Prevalence: the proportion of participants who have at least one positive ADA sample (baseline or post-baseline) among all participants evaluable for ADA prevalence.

ADA Incidence: the proportion of participants who have treatment-emergent ADA among all participants evaluable for ADA incidence.

Treatment-Emergent ADA: either treatment-boosted or treatment-induced ADA.

Treatment-Boosted ADA: defined as positive baseline ADA sample and at least one positive post-baseline ADA sample and $(\text{the max titer of the post-baseline ADA}) / (\text{titer of baseline ADA}) \geq 4$. Also, if baseline is positive and titer is less than limit of detection and post-baseline titer is equal to or greater than limit of detection, it is considered treatment-boosted. The proportion of participants who have treatment-boosted ADA is calculated based on the total number of participants evaluable for ADA incidence as the denominator.

Treatment-Induced ADA: defined as negative or missing baseline ADA sample and at least one positive post-baseline ADA sample. The proportion of participants who have treatment-induced ADA is calculated based on the total number of participants evaluable for ADA incidence as the denominator.

Persistent ADA: defined as a) treatment-induced ADA detected at two or more sampling time points during the study, where the first and last ADA-positive sample (irrespective of any negative samples in between) are separated by a period of 16 weeks or longer; or b) treatment-induced ADA detected at the last sampling time point of the study. The proportion of participants who have persistent ADA is based on the total number of participants evaluable for ADA incidence as the denominator.

Transient ADA: defined as treatment-induced ADA that does not meet the definition of persistent ADA. The proportion of participants who have transient ADA is based on the total number of participants evaluable for ADA incidence as the denominator.

Participant-level ADA status: defined as “ADA+” if the participant has treatment- emergent ADA; “ADA-” if the participant is evaluable for ADA incidence and does not have treatment-emergent ADA; missing if the participant is not evaluable for ADA incidence.

Time to ADA onset: for participants with treatment-induced ADA, defined as the number of days after first dose to the day when the first positive ADA result was detected; for participants with treatment-boosted ADA, defined as the number of days after first dose to the day when the first boosted post-baseline positive ADA result was detected. A post-baseline positive ADA result is boosted if $(\text{titer of the post-baseline ADA}) / (\text{titer of baseline ADA}) \geq 4$.

